### Progression-free Survival (PFS)

- Analysis set: Response Evaluable

Progression-free survival (PFS) is defined as the time from date of the first dose of study treatment to the earliest documented disease progression by Investigator assessment, or death due to any cause, whichever occurs first. If a patient has not had a PFS event at the time of the analysis cutoff or at the start of any new anticancer therapy, PFS is censored at the date of last adequate tumor assessment.

PFS will be calculated as follows:

$$\text{PFS (months)} = (\text{date of event or censoring} - \text{date of first dose} + 1) / 30.4375$$

The censoring and event date options to be considered for PFS analysis are presented in Table 2.

PFS time will be estimated using the Kaplan-Meier method. The PFS rate at 3, 6, 9, 12, 15 and 18 months will be estimated with corresponding 2-sided 95% CIs.

Frequency (number and percentage) of participants with each event type (PD or death) and censoring reasons will be presented along with the overall event and censor rates. Reasons for censoring will be summarized according to the categories in [Table 3](#). In addition, time to progression/censoring, event, and censoring reasons will be listed.

**Table 2 PFS and DOR Outcome and Event Dates**

Situation	Date of Progression/Censoring	Outcome
No adequate baseline assessment a	Date of first dose a	Censored a
PD or death - after at most one missing or inadequate postbaseline tumor assessment, or - $\leq 8$ weeks ( $\pm 3$ -day window) after date of first dose	Date of PD or death	Event
PD or death - after $\geq 2$ missing or inadequate postbaseline tumor assessment	Date of last adequate tumor assessment b documenting no PD prior to new anticancer therapy, or missed tumor assessments	
No PD		Censored
New anticancer therapy given prior to PD or death		

a This criterion only applies to PFS censoring. If the participant dies  $\leq 6$  weeks after date of first dose and did not initiate new anticancer therapy, the death is an event with date on death date (6 weeks is 2 times the length of the first 2 tumor assessment intervals).

b If there are no adequate post-baseline assessments prior to the PD or death, then the time without adequate assessment should be measured from the date of first dose; if the criteria is met, the censoring will be on the date of first dose.

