Visit Window (days)		±2			±2	±2	±2	±2	±2	±2		±7		±7	
 Additional visit window may be allowed after discussion and agreement between investigator and sponsor. 
a. End of inpatient observation (PK, ECG, vital signs).
 
b. PK/PD and ECG only.

Inpatient observation		X	X	X		X		(X)		(X)					
 Participants will be observed inpatient for at least 48 hours after the first SC dose (or the first IV dose administration, as applicable) on C1D1 and for at least 8 hours after the second SC dose (or the second IV dose administration, as applicable) on C1D15. See Section 4.1. Participants who experience ≥ Grade 3 infusion-related adverse events (IV administration) or clinically significant CRS must be hospitalized for at least 24 hours for at least 4 doses subsequently (two cycles). See Section 4.1. See Section 6.1 for additional information.

Table 1. Study Schedule of Assessments – Part 1 Without Priming

Visit Identifier Abbreviations used in this table may be found in Appendix 17	Screening	Treatment Period										EOT	4-week Follow- up	90-day Follow- up for irAEs	Notes
		Cycle 1 = 28 days					Cycle ≥2 (28 days)								
Study Day	-28 to -1	1	2	3 ^a	8	15 ^a	22	1	C3D8 ^b	15					
Visit Window (days)		±2			±2	±2	±2	±2	±2	±2		±7	±7		
 Additional visit window may be allowed after discussion and agreement between investigator and sponsor. 
a. End of inpatient observation (PK, ECG, vital signs).
 
b. PK/PD and ECG only.

Injection site tolerability assessment		X	X			X		As clinically indicated							
 C1D1: at least 1 hour and 24 hours (±1 hr) after SC injection. C1D15: at least 1 hour after SC injection. See Section 8.2.6 for additional information.
Efficacy Assessment															
Tumor response assessment	X	Performed every 8 weeks from C1D1 (±7 days) for the first 6 months, every 12 weeks (±7 days) for the next 18 months, and every 4 months thereafter.								X					
 CT/MRI scans of head, chest, abdomen, pelvis, any clinically indicated sites of disease (see Section 8.1.1).
Bone scan or PET	X	Performed every 8 weeks from C1D1 (±7 days) for the first 6 months, every 12 weeks (±7 days) for the next 18 months, and every 4 months thereafter.								X					
 For bone metastasis (see Section 8.1.1).
Safety Assessment															

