8.1. Efficacy Assessments

8.1.1. Tumor Response Assessments

Tumor assessments will include all known or suspected disease sites. Imaging will include contrast enhanced head, chest, abdomen, and pelvis computed tomography or MRI scans; brain computed tomography or MRI scan for participants with known or suspected brain metastases; bone scan and/or PET scan for all participants to monitor potential bone metastases. For participants with known computed tomography contrast allergy, a non-

contrast computed tomography of the chest with contrast enhanced abdominal and pelvic MRI can be used. The same imaging technique used to characterize each identified and reported lesion at baseline will be employed in the following tumor assessments.

Antitumor activity will be assessed through radiological tumor assessments conducted at baseline, during treatment every 8 weeks from C1D1 (± 7 days) for the first 6 months, every 12 weeks (± 7 days) for the next 18 months, and every 4 months thereafter as specified in the [SOA](#), whenever disease progression is suspected (eg, symptomatic deterioration), and at the time of withdrawal from treatment (if not done in the previous 4 weeks). Assessment of response will be made using RECIST version 1.1 (see [Appendix 12](#)) and irRECIST (See [Appendix 13](#)). Confirmation of response (CR/PR) with a second consecutive scan at least 4 weeks later is preferred.

All participants' files and radiologic images must be available for source verification and for potential peer review.

Antitumor activity will be assessed at baseline, during treatment as specified in the [SOA](#), whenever disease progression is suspected (eg, symptomatic deterioration), and at the time of withdrawal from treatment (if not done in the previous 4 weeks).

If imaging is used in disease assessment, the same imaging technique used to characterize each identified and reported lesion at baseline will be employed in post-baseline disease assessments.

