- **Progressive Disease (PD):** Progression documented within 12 weeks after 'start date' and not qualifying as CR, PR or SD.
- **Not Evaluable (NE):** All other cases. Note that reasons for NE should be summarized and the following reasons could be used:
  - No adequate baseline assessment
  - No evidence of disease at baseline
  - No post-baseline assessments due to early death, i.e., death prior to 6 weeks after 'start date'.
  - No post-baseline assessments due to other reasons
  - All post-baseline assessments have overall response NE
  - New anti-cancer therapy started before first post-baseline assessment
  - SD of insufficient duration (<5 weeks after 'start date' without further evaluable tumor assessments)
  - PD too late (>12 weeks after start of treatment)
  - Special and rare cases where BOR is NE due to both SD of insufficient duration ('too early') and late PD will be classified as 'SD of insufficient duration.'

- Unconfirmed CR (uCR) is defined as one objective status of CR documented before PD.
- Unconfirmed PR (uPR) is defined as one objective status of PR documented before PD but not qualifying as uCR.

Note: An objective status of PR, SD, or Non-CR/Non-PD cannot follow one of CR. SD can follow PR only in the rare case that tumor increases by less than 20% from the nadir, but enough that a previously documented 30% decrease from baseline no longer holds. If this occurs the sequence PR – SD – PR is considered a confirmed PR. A sequence of PR – SD – SD – PD would be a best response of SD if the window for SD definition has been met.

Patients with a BOR of “Not Evaluable” (NE) based on confirmed responses will be summarized by reason for having unknown status. The following reasons will be used:

- No adequate baseline assessment.
- No post-baseline assessments due to early death .
- No post-baseline assessments due to COVID-19 (ie, patients miss tumor assessment visits due to COVID-19 pandemic).
- No post-baseline assessments due to other reasons.
- All post-baseline assessments have overall response NE.
- New anticancer therapy started before first post-baseline assessment.
- SD of insufficient duration (<6 weeks after date of the first dose without further evaluable tumor assessments).
- PD >12 weeks after date of the first dose (ie, tumor assessment of PD was >12 weeks after date of the first dose and there was no tumor assessment in between).

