Special and rare cases where BOR is NE due to both SD of insufficient duration (SD <6 weeks after date of the first dose) and late PD (PD >12 weeks after date of the first dose) will be classified as “SD of insufficient duration”.

- Tumor response will be presented in the form of participants data listings that include, but are not limited to: tumor type, actual received day 1 dose, tumor response at each assessment, and best overall response. Progression date, death date, date of first response, last assessment date, and date of last contact will also be listed. Additionally, a graphical representation (swimmer plot) will be provided to display tumor response overtime and a waterfall plot displaying the best percentage change in tumor size will be provided.
- Missing data: Data after the study intervention is discontinued and rescue will be excluded; intermediate missing values (ie, values collected between baseline and the last study measurement) will not be imputed.

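### SAP Table 2's 6-week early-death limit and the 12-week PD limit for best response do not match the 8-week scan schedule, and the minimum SD duration is given as both 5 and 6 weeks

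*SAP*

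**What the plan says.** **Scan schedule.** Protocol 8.1.1 has "radiological tumor assessments conducted at baseline, during treatment every 8 weeks from C1D1", and the schedule in Protocol 1.3.1 reads "Performed every 8 weeks from C1D1 (±7 days) for the first 6 months". The interval then lengthens to 12 weeks for the next 18 months.

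**PFS rules.** In SAP Table 2, a participant with no adequate baseline assessment is censored at first dose. Footnote a to that row begins "This criterion only applies to PFS censoring". It then makes one exception: a death within 6 weeks of first dose, with no new anticancer therapy, counts as an event. The reason given for 6 weeks is that "6 weeks is 2 times the length of the first 2 tumor assessment intervals". For everyone else, PD or death is an event if it follows at most one missing or inadequate scan, or if it falls within 8 weeks (±3 days) of first dose.

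**Best overall response.** SAP 6.2.4 allows a BOR of PD only when progression is documented within 12 weeks. The first list of NE reasons has "PD too late (>12 weeks after start of treatment". The second list repeats the limit and adds that no assessment took place in between.

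**Minimum SD duration.** The SD definition in SAP 6.2.4 requires 6 weeks. The first NE list has "SD of insufficient duration (<5 weeks after 'start date' without further evaluable tumor assessments". The second list uses 6 weeks, as does the sentence after it: "SD of insufficient duration (SD <6 weeks after date of the first dose". The separate non-CR/non-PD category uses 5 weeks.

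**Analysis set.** PFS uses the Response Evaluable Set. SAP Table 1 requires measurable disease at baseline and at least one post-baseline assessment for that set. Protocol 9.2 instead requires an adequate baseline assessment.

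**The concern.** Footnote a states a piece of arithmetic that is false for this trial, and a censoring rule rests on it. The 12-week PD limit falls between the first two scheduled scans, so BOR tolerates no missed first scan while the PFS rule in the same SAP tolerates one. The same participant can then be a progressor for PFS and NE for BOR. The proportion with PD is a listed binary endpoint with exact confidence intervals (SAP 5.2.1), and the reasons for NE are to be tabulated, so reported tables are affected. The two SD limits for the same NE reason cannot both be programmed.

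**Working it through.** **1. The stated figure.** The input is the 8-week interval with a ±7-day window (Protocol 8.1.1 and 1.3.1).
- Two intervals: 2 × 8 = 16 weeks; with the window, 16 + 1 = 17 weeks.
- Most literal reading (twice the sum of the first two intervals): 2 × (8 + 8) = 32 weeks.
- Later 12-week interval: 2 × 12 = 24 weeks.
- Working backwards: 6 / 2 = 3, so 6 weeks would need scans every 3 weeks.

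No reading reproduces 6 weeks.

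**2. Limits against in-window scan times.** Scan 1 falls at weeks 7–9, scan 2 at weeks 15–17 and scan 3 at weeks 23–25.

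| Limit | Position | Result |
|---|---|---|
| 6 weeks (footnote a) | before scan 1 | less than one interval |
| 12 weeks (BOR PD) | between scans 1 and 2 | covers one scan only |
| 5 or 6 weeks (SD minimum) | before scan 1 | every in-window scan passes both |

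**3. BOR and PFS for the same participant.**

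| Course | BOR as written | BOR, 16-week limit | BOR, 17-week limit | PFS, SAP Table 2 |
|---|---|---|---|---|
| PD at week 8 | PD | PD | PD | event |
| SD at week 7, PD at week 16 | SD | SD | SD | event |
| Week-8 scan missed, PD at week 15 or 16 | NE | PD | PD | event |
| Week-8 scan missed, PD at week 17 | NE | NE | PD | event |

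The last two rows are PFS events because only one scan was missed. A 16-week limit would still leave an in-window PD at week 17 as NE, so 17 is the figure needed.

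**4. The 5/6-week conflict.** Take SD on an unscheduled scan at week 5.5, a missed week-8 scan, and PD at week 16. Under the 12-week PD limit, BOR is SD with a 5-week minimum and NE with a 6-week minimum. With scheduled scans the two never differ.

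**5. The ±3-day window.** With no post-baseline scan, an event up to week 16 follows at most one missed scan. The count rule therefore already makes it an event, and changing ±3 to ±7 days alters no classification.

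**6. Size of the BOR effect.** Assume exponential PFS and a share m who miss the week-8 scan. Sixteen weeks is 112 / 30.4375 = 3.68 months, and P(PFS event by week 16) = 1 − 0.5^(3.68 / median). The 5.4-month median is the first-line TNBC figure in Protocol 4.2.2. The 2- and 3-month medians and all values of m are assumptions.

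| Median PFS (months) | P(event by week 16) | 20 × m × P, m = 5% | m = 10% | m = 20% |
|---|---|---|---|---|
| 2 | 0.721 | 0.72 | 1.44 | 2.88 |
| 3 | 0.573 | 0.57 | 1.15 | 2.29 |
| 5.4 | 0.376 | 0.38 | 0.75 | 1.51 |

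This leans high, because it counts deaths as PD and ignores PD found on an unscheduled scan before week 12. One participant of 20 is 1 / 20 = 5 percentage points.

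**7. Size of the footnote a effect.** Assume exponential OS, with P(death in weeks 6–16) = 0.5^(1.38 / median) − 0.5^(3.68 / median), in months. For medians of 6, 12 and 17.5 months this gives 0.199, 0.115 and 0.082. These are shares of inadequate-baseline participants only. If a cohort of 20 held one such participant (assumption), about 0.1 to 0.2 participants would be affected.

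**The case against.** The strongest reply has three parts.

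*Footnote a governs an almost empty group.* This stands. To be affected, a participant needs measurable disease but an inadequate baseline assessment, then a post-baseline assessment, then death by about week 16 or 17 without new therapy. Under the protocol's definition of the set there would be none. A reader might infer that PFS is materially biased upward by deaths censored at first dose; the documents do not support that. The same facts also show that the exception does not work as written. The earliest in-window scan is week 7, so without an unscheduled scan someone who dies by week 6 is not in the PFS set at all.

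*The 12-week limit is a choice, not an arithmetic slip.* This stands in part. The SAP never says that 12 weeks is two intervals, it states the limit consistently, and BOR and PFS may have different rules. However, the SAP gives no reason for tolerating one missed scan in PFS and none in BOR, and the limit sits in a gap where no scan is scheduled.

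*Nothing important changes.* ORR and the disease control rate are indeed unaffected, because PD and NE both count as neither response nor disease control. There is also no hypothesis test. The PD proportion and the NE reasons do change.

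A reader might also infer that none of the limits fits the schedule, or that events are widely censored. Neither holds. The 5- and 6-week minimums are met by every scheduled scan, and they conflict only with each other. For participants with an adequate baseline, the SAP Table 2 count rule keeps PD or death after one missed scan as an event.

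**Conclusion.** The concern holds in a limited form.

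- The 6-week figure in footnote a is wrong for an 8-week schedule; two intervals are 16 weeks, or 17 with the window. The practical effect on PFS is very small, roughly 0.1 to 0.2 participants per cohort even if one participant per cohort lacked an adequate baseline.
- The 12-week PD limit makes BOR NE for PD at weeks 15–17 after a missed or inadequate week-8 scan, while the same PD is a PFS event. On the assumptions shown, this is about 0.4 to 2.9 of 20 participants per cohort, moving only between PD and NE. That ORR and the disease control rate are unchanged assumes NE participants stay in the denominator.
- The 5- versus 6-week SD minimum is a self-contradiction that matters only for unscheduled early scans.

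The arithmetic error and the two rule conflicts are certain from the text. Their sizes depend on the missed-scan rate and on event times, which the documents do not give for these cohorts.

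**What to change.** These are SAP wording changes, best made before programming:

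- In SAP Table 2 footnote a, replace 6 weeks with 17 weeks, and state the reason as two 8-week intervals plus the 7-day window.
- In SAP 6.2.4, set the PD limit to 17 weeks in the BOR definition, in both NE lists and in the sentence on combined early SD and late PD.
- Use 6 weeks as the single minimum SD duration, which means changing the 5 in the first NE list. The 5-week minimum for non-CR/non-PD belongs to a separate category; keep it only if the difference is intended.
- As tidy-up, replace the ±3-day window in SAP Table 2 with the protocol's ±7 days. This has no effect on classification.

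The cost is that a few participants move from NE to PD and, rarely, one moves from censored to event. No data collection changes.

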**Table 3 PFS Censoring Reasons and Hierarchy**

Hierarchy	Condition	Censoring Reason
1	No adequate baseline assessment	No adequate baseline assessment
2	Start of new anticancer therapy before event	Start of new anticancer therapy
3	Event after 2 or more missing or inadequate postbaseline tumor assessment/start date	Event after missing or inadequate assessments
4	No event and [withdrawal of consent date $\geq$ date of first dose OR End of study (EOS) = Subject refused further follow-up]	Withdrawal of consent
5	No event and lost to follow-up in any disposition page	Lost to follow-up
6	No event and lost to follow-up in any disposition page	No adequate post-baseline tumor assessment
7	No event and none of the conditions in the prior hierarchy are met	Ongoing without an event

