9.2. Analysis Sets

For purposes of analysis, the following analysis sets are defined.

Participant Analysis Set	Description
Full Analysis Set (FAS)	All enrolled participants.
Safety Analysis Set (SAS)	All enrolled participants who receive at least 1 dose of study intervention. Unless otherwise specified the safety analysis set will be the default analysis set used for all analyses.
Per Protocol Analysis Set	All enrolled participants who do not have major protocol deviations during the course of the study
DLT Evaluatable Set	All enrolled participants who had at least 1 dose of study treatment and either experienced DLT or do not have major protocol deviations during the DLT observation period.
mITT Population	All enrolled participants who have received at least 1 dose of study medication; have a baseline assessment and at least 1 post baseline assessment;
PK Parameter Set	All enrolled participants treated who do not have protocol deviations influencing PK assessment and have sufficient information to estimate at least 1 of the PK parameters of interest.
PK Concentration Set	All enrolled participants who are treated and have at least 1 analyte concentration above the lower limit of quantitation.
Response Evaluatable Set	All enrolled participants who received at least 1 dose of study treatment and had adequate baseline disease assessment. Participants who discontinued early or died will be included.
Pharmacodynamic/ Biomarker Analysis Set(s)	The Pharmacodynamic/Biomarker analysis population is defined as all enrolled participants with at least 1 of the Pharmacodynamic/Biomarkers evaluated at pre and/or post dose.
Immunogenicity Analysis Set	The immunogenicity analysis set includes all enrolled participants who received at least 1 dose of study treatment and have at least 1 sample tested for ADA.

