**Table 1. Analysis Sets**

Participant Analysis Set	Description
Full Analysis Set (FAS)	All enrolled participants.

Participant Analysis Set	Description
Safety Analysis Set (SAS)	All enrolled participants who receive at least 1 dose of study intervention. Unless otherwise specified the safety analysis set will be the default analysis set used for all analyses.
Per Protocol Analysis Set	All enrolled participants who do not have major protocol deviations during the course of the study
DLT Evaluable Set	All enrolled participants who had at least 1 dose of study treatment and either experienced DLT or do not have major protocol deviations during the DLT observation period and received either 100% of dosing in cycle 1 (no priming regimen) or 100% of dosing in cycle 1 and cycle 2 (priming regimen)..
mITT Population	All enrolled participants who have received at least 1 dose of study medication; have a baseline assessment and at least 1 post baseline assessment;
Response Evaluable set	The response evaluable population will include all participants who received at least one dose of study treatment and had measurable disease at baseline and at least one post baseline disease assessment.
PK Parameter Set	All enrolled participants treated who do not have protocol deviations influencing PK assessment and have sufficient information to estimate at least 1 of the PK parameters of interest.
PK Concentration Set	All enrolled participants who are treated and have at least 1 analyte concentration above the lower limit of quantitation.

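### SAP Table 3 gives rows 5 and 6 the same condition, so the reason for no adequate post-baseline tumor assessment can never be assigned, and the participants meant for it are labelled as ongoing

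*SAP*

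**What the plan says.** SAP Section 6.2.4, under Progression-free Survival, points to Table 3 for the reported reasons ("Reasons for censoring will be summarized according to the categories in"). It also calls for frequencies of each censoring reason and a participant listing of times and reasons. Table 3 is titled "PFS Censoring Reasons and Hierarchy" and ranks its rows 1 to 7. The last three rows work as follows.

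- Row 5 has the condition "No event and lost to follow-up in any disposition page". The reason it reports is loss to follow-up.
- Row 6 repeats row 5's condition word for word, yet the reason it reports is a different one: "No adequate post-baseline tumor assessment".
- Row 7 is the catch-all. Its condition is "No event and none of the conditions in the prior hierarchy are met", and it labels the participant as ongoing with no event.

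The population is given as "Analysis set: Response Evaluable". The two documents define that set differently. SAP Table 1 requires that a participant "had measurable disease at baseline and at least one post baseline disease assessment". Protocol Section 9.2 requires a dose and an adequate baseline disease assessment but nothing after baseline, and adds: "Participants who discontinued early or died will be included".

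**The concern.** The condition in row 6 does not mention tumor assessments, so it cannot define the reason beside it. It looks like row 5's text carried down one line. Nothing else in the SAP or protocol supplies another condition for row 6.

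A censoring-reason table lets a reader judge how much of the PFS censoring is administrative, meaning the participant was still being followed at the cutoff, and how much reflects missing disease information. A participant with no usable post-baseline scan belongs to the second kind. If the table is programmed literally, that participant is counted in the category a reader will take as the first kind.

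**Working it through.** There is no sample size, power or error rate to reproduce here, so the check is one of table logic.

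**Inputs.** The seven conditions in SAP Table 3, read in rank order with the first match deciding the reason. Row 7 supports that reading, because it is defined by failure to meet the rows above it.

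**Rows 5 and 6 directly.** Let A be the set of participants with no event who are lost to follow-up. Row 5 takes A. Row 6 is offered A minus A, which is empty. Row 6 is therefore never assigned, whatever the data.

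**Enumeration.** Seven yes/no facts settle the outcome: no adequate baseline, new anticancer therapy, an event, two or more missed or inadequate assessments before it, consent withdrawn, lost to follow-up, and no adequate post-baseline assessment. They give 2^7 = 128 combinations. Each was passed through the table twice. The first pass used row 6 as written. The second used the condition its label implies (an assumption): no event and no adequate post-baseline assessment.

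| Outcome | Row 6 as written | Row 6 as its label implies |
|---|---|---|
| Row 1, no adequate baseline | 64 | 64 |
| Row 2, new anticancer therapy | 32 | 32 |
| Row 3, event after missed assessments | 8 | 8 |
| Row 4, consent withdrawn | 8 | 8 |
| Row 5, lost to follow-up | 4 | 4 |
| Row 6, no adequate post-baseline assessment | 0 | 2 |
| Row 7, ongoing | 4 | 2 |
| Counted as an event | 8 | 8 |
| Total | 128 | 128 |

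The only change is that two combinations move from row 7 to row 6. Both have an adequate baseline, no new therapy, no event, consent not withdrawn, no loss to follow-up and no adequate post-baseline assessment. They differ only in the missed-assessment flag, which matters only when there is an event. These are counts of logical combinations, not expected numbers of participants.

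**Who is affected.** There are 64 combinations with no event (2^6), and half of them, 32, have no adequate post-baseline assessment. As written, those 32 split as 16 to row 1, 8 to row 2, 4 to row 4, 2 to row 5 and 2 to row 7. Only the last 2 are mislabelled; the other 30 keep their reason under either version.

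**Whether such participants can be in the analysis.**

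- SAP Table 1 requires a post-baseline assessment but does not say it must be adequate.
- Protocol Appendix 12 describes how an assessment becomes indeterminate: lesions not assessed, methods inconsistent with baseline, or lesions that cannot be measured accurately.
- The best-overall-response rules in SAP Section 6.2.4 list, as a reason for being not evaluable, that every post-baseline assessment was itself not evaluable.

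The SAP therefore provides for this kind of participant. Under the protocol's set, participants with no post-baseline scan at all would join them.

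**The case against.** The strongest reply is that this is a copying slip with an obvious remedy. The label shows what row 6 was for, and a careful programmer would ask. The same information also appears elsewhere. Reasons for a not-evaluable best response are summarized, treatment and study discontinuations are tabulated with reasons, and the PFS listing puts each censoring time beside its reason, so a very short time labelled as ongoing would stand out. This limits the harm. It does not make the rule right: literal programming gives a wrong table, and silent correction departs from the SAP without a record.

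Three stronger readings are tempting, and the documents do not support them.

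- **That everyone without a usable scan is reported as ongoing.** Those who withdrew consent, were lost to follow-up or started new therapy keep those reasons either way. A participant who stops early with no post-baseline scan is outside the SAP's Response Evaluable Set, so is not in the table. Protocol Section 8.1.1 also calls for a scan at withdrawal if none was done in the previous 4 weeks. That example works only under the protocol's wider set.
- **That the size can be given in percentage points.** One participant in 20 is 5 points, but 20 is planned enrollment per Part 2 cohort, not the size of the Response Evaluable Set, and the number affected is not given. It could be zero.
- **That PFS itself is biased.** Event status and dates are set by SAP Table 2, without reference to the reason in Table 3.

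**Conclusion.** Wrong as written. Row 6 of SAP Table 3 cannot be assigned, and every participant it was meant for who passes rows 1 to 5 is reported as ongoing without an event. Under the SAP's analysis set these are participants whose post-baseline assessments were all inadequate; under the protocol's set they also include those never scanned after baseline.

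The number affected cannot be stated from the documents. The error is confined to the PFS censoring-reason summary and listing. Medians, PFS rates and Kaplan-Meier curves do not change, and the study has no formal hypothesis test that could be affected. The point is minor in consequence but definite.

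It rests on two assumptions: that the ranked table is applied first match first, and that row 6 was meant to carry the condition its own label describes. The documents do not state the second, but the label leaves little room for another reading.

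**What to change.** Replace the condition in row 6 of SAP Table 3 with one that matches its reason: the participant has no PFS event and has no adequate tumor assessment after baseline. Leave the order of the rows as it is, and leave row 7 as the catch-all.

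Row 7 does not need to be redesigned to correct this error. Restricting it to participants still in tumor follow-up, with an added row for those who stopped treatment without progression and had no further assessments, would be a change of preference. It would also leave some participants with no category: for example, someone who stopped treatment without progression, had some further scans and then left tumor follow-up.

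The cost is one table cell in a SAP revision, ideally before the PFS outputs are programmed. Study conduct, data collection and PFS estimates are unaffected.
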